2.2.1 General Study Design

A series of 15 patients undergoing geniculate artery embolization will be included in this arm with the explicit purpose to demonstrate safety and efficacy.

This trial will assess reduction in pain, functional improvement, and reduction of conservative medical therapy in patients with mild to moderate knee osteoarthritis who have failed conservative

management, for 6 months and for up to two years following embolization.

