Subjects will not initiate new pain therapy or escalate current therapy for 1 month prior to GAE. A dose of intravenous antibiotic will be given in the peri-procedural period and oral antibiotics may be continued for up to 7 days. Anti-inflammatory medications will also begin 1 day prior to and up to 7 days after the procedure.

On the day of the procedure, the subject will be brought to the angiography suite and positioned in the supine position. Anxiolytic medications and analgesics will be administered per patient and provider discretion. After appropriate local anesthesia, arterial access will be obtained using a standard micropuncture kit. The femoral artery ipsilateral to the affected knee will be catheterized. A subsequent angiogram will be used to identify abnormal neovascularization arising from the geniculate artery branches. The affected geniculate artery branches will be catheterized with a microcatheter and the abnormal vessels will be embolized with a suspension of the Gel-Bead particles ranging in size from 100 to 500 micrometers at the physician's discretion. The suspension will slowly be injected into the vessel until there is stasis of forward flow. All guidewires, catheters and microcatheters will be removed. Hemostasis will be obtained either with manual compression or a closure device.

The following data will be collected during each GAE procedure:

- Technical success of GAE, defined as successful catheterization and embolization
- Procedure time, duration of hospitalization, duration of catheterization, fluoroscopy dose, volume of embolic delivered, arteries embolized.

Post-procedure Care and Disposition:

Following the procedure, the patient will be observed in the post-procedure area. Routine postangiography care will be provided and routine precautions followed (lying flat for up to 6 hours post procedure, adequate post-procedure hydration with intravenous fluids). No additional lab work will be routinely drawn at this time. Any additional labs drawn will be left to the discretion of the attending physician. All complications, minor and major, will be documented and managed appropriately at the physician's discretion. Patient may be deemed appropriate discharge on the same day if:

- 1. There are no access site complications (e.g. groin hematoma)
- 2. Pain is adequately controlled
- 3. Patient is ambulatory
- 4. Distal perfusion to the bilateral lower extremities is confirmed by physical examination and/or Doppler waveforms

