2.4.2.1 Study Compliance

Subjects will be required to avoid escalation of conservative therapy during the study period. A review of current and prior conservative treatment measures will be reviewed with each subject during follow-up visits. Any patient that significantly elevates conservative therapy (e.g. initiation of a new medication or therapy not previously used) will be withdrawn from the study.

Early Withdrawal of Subjects:

Subjects will be withdrawn from the study under the following conditions:

- 1 At any point at the patient's discretion
- 2 Any major complication that occurs that prevents the ability to perform/complete the GAE procedure
- 3 Patient is unable to complete at least one follow-up visit

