3.2 Adverse Event Recording/Reporting

3.2.1 Adverse Event Definitions

Adverse effect. Any untoward medical occurrence in a clinical study of an investigational device; regardless of the causal relationship of the problem with the device or, if applicable, other study treatment or diagnostic product(s).

Associated with the investigational device or, if applicable, other study treatment or diagnostic product(s). There is a reasonable possibility that the adverse effect may have been caused by the investigational device or, if applicable, the other study treatment or diagnostic product(s).

Disability. A substantial disruption of a person's ability to conduct normal life functions.

Life-threatening adverse effect. Any adverse effect that places the subject, in the view of the investigatorsponsor, at immediate risk of death from the effect as it occurred (i.e., does not include an adverse effect that, had it actually occurred in a more severe form, might have caused death).

Serious adverse effect. Any adverse effect that results in any of the following outcomes: death, a lifethreatening adverse effect, inpatient hospitalization or prolongation of existing hospitalization, a persistent or significant disability/incapacity, or a congenital anomaly/birth defect.

Hospitalization shall include any initial admission (even if less than 24 hours) to a healthcare facility as a result of a precipitating clinical adverse effect; to include transfer within the hospital to an intensive care unit. Hospitalization or prolongation of hospitalization in the absence of a precipitating, clinical adverse effect (e.g., for a preexisting condition not associated with a new adverse effect or with a worsening of the preexisting condition; admission for a protocol-specified procedure) is not, in itself, a serious adverse effect.

Unexpected adverse effect. Any adverse effect, the frequency, specificity or severity of which is not consistent with the risk information described in the clinical protocol(s) or elsewhere in the current IDE application, as amended.

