3.3 Withdrawal of Subjects due to Adverse Effects

During evaluation of subjects and visits after the procedure, any adverse effects due to treatment will be evaluated and monitored. Subjects will not be withdrawn from the study due to adverse effects.

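### The rule withdrawing subjects whose GAE is prevented or stopped by a major complication conflicts on its face with section 3.3, ends their scheduled follow-up, and leaves their place in the safety analysis unstated

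*Combined protocol and SAP*

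**What the plan says.** Section 2.4.2.1, under early withdrawal, opens its list with "Subjects will be withdrawn from the study under the following conditions". The second condition is "Any major complication that occurs that prevents the ability to perform/complete the GAE procedure". The subject leaves the study, not only the treatment.

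Section 3.3 states the opposite rule: "Subjects will not be withdrawn from the study due to adverse effects". The sentence before it reads "During evaluation of subjects and visits after the procedure, any adverse effects due to treatment will be evaluated and monitored".

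Section 2.2.1 says that the series "will be included in this arm with the explicit purpose to demonstrate safety and efficacy". For each procedure, the text on Visit 2 (section 2.4) lists among the data to be collected "Technical success of GAE, defined as successful catheterization and embolization".

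On recording, the post-procedure text in section 2.4 has every complication documented, whether minor or major. Section 3.1 has all adverse events documented and reported to the IRB. Section 3.2.3 has all adverse effects recorded whatever their suspected cause, and follows those felt to be associated with the device or other study treatment until they resolve or stabilize.

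On analysis, section 2.5.3 compares baseline and endpoint scores with paired t-tests. Section 2.5.4 summarises adverse events descriptively in the pilot group. Neither section defines an analysis set, and no rule for missing data is given.

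**The concern.** A subject whose procedure is stopped by a major complication has had one of the worst procedural outcomes that the study can produce. Safety is a stated purpose, so this is the subject whose later course matters most. If the withdrawal condition is applied as written, that subject leaves the study on the day of the procedure and the scheduled visits lapse.

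There is a second exposure. The event that triggers withdrawal can also be a technical failure. With no stated denominator for adverse events or technical success, whoever writes the report can count such subjects or leave them out, and leaving them out makes both rates look better. In a series of 15 or 30, one subject decides whether the report shows a major complication at all.

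**Working it through.** The plan states no figure on this point, so there is none to reproduce. The check is a comparison of texts followed by an illustration.

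**1. Do the two rules meet on the same event?** Section 3.2.1 defines an adverse effect as "Any untoward medical occurrence in a clinical study of an investigational device; regardless of the causal relationship". A major complication that aborts GAE falls within that definition. One section therefore requires withdrawal and the other forbids it, unless section 3.3 is limited to effects found after the procedure. Its lead-in allows that reading, but the prohibition itself carries no such limit.

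**2. What does withdrawal take away?**
- Section 3.2.2 has adverse effects elicited at study visits. Section 2.4 places the adverse event reviews and KOOS at Visits 4, 5 and 6 (1, 3 and 6 months). A subject withdrawn at Visit 2 has none of these.
- The follow-up in section 3.2.3 continues for effects already identified as associated with device or treatment. It schedules no questioning about new or delayed effects.
- The paired t-test needs a 6-month score. Without one, the subject drops out of that comparison.
- Section 2.3.2 expects every enrolled subject to complete, so the plan makes no allowance for these withdrawals.

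**3. What does withdrawal not take away?** The complication is still documented, recorded and reported (sections 2.4, 3.1 and 3.2.3). Technical success is among the data collected at each procedure. No text deletes data from withdrawn subjects or removes them from a denominator.

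**4. How much could the open denominator matter?** Assume x complications that stop GAE before embolization, among n subjects. The documents give both 15 (sections 2.2.1, 2.5.2 and 3.1) and 30 (section 2.3.2; up to 30 in section B), so both sizes are shown. If the affected subjects are kept, the rate is x/n; if they are dropped, it is 0/(n − x). Limits are exact two-sided 95% (Clopper-Pearson). With zero events the upper limit is 1 − 0.025^(1/m), where m is the number of subjects left:
- m = 14: 1 − 0.025^(1/14) = 23.2%
- m = 29: 1 − 0.025^(1/29) = 11.9%

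| n | Assumed events | Kept (95% CI) | Dropped (upper limit) |
|---|---|---|---|
| 15 | 1 | 1/15 = 6.7% (0.2% to 31.9%) | 0/14 = 0% (23.2%) |
| 15 | 2 | 2/15 = 13.3% (1.7% to 40.5%) | 0/13 = 0% (24.7%) |
| 30 | 1 | 1/30 = 3.3% (0.1% to 17.2%) | 0/29 = 0% (11.9%) |
| 30 | 2 | 2/30 = 6.7% (0.8% to 22.1%) | 0/28 = 0% (12.3%) |

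With one such event, technical success reads 14/15 = 93.3% if the subject is kept and 14/14 = 100% if dropped. At 30 it reads 29/30 = 96.7% against 29/29 = 100%.

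**5. How likely is at least one event?** The documents give no planning rate; section 1.0 says small earlier trials saw no major complications. For assumed true rates p of 2%, 5% and 10%, 1 − (1 − p)^n gives 26%, 54% and 79% at n = 15, and 45%, 79% and 96% at n = 30.

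**The case against.** The strongest reply is that nothing is hidden. A reader might infer that the withdrawal condition removes the worst procedural outcomes from the trial, and so biases both the complication rate and technical success in favour of GAE. The documents do not support that. The recording duties set out above contain no exception for withdrawn subjects, and the event occurs before withdrawal can take effect. An injury during the procedure would ordinarily be judged associated with study treatment, and so followed until resolved or stable. The adverse event summary covers the pilot group and excludes nobody. Bias arises only if the analyst chooses to omit these subjects. All of this stands.

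A reader might also infer that the two rules can never both be followed. That too goes further than the text. The withdrawal condition can be read as covering aborted procedures, and section 3.3 as covering effects found at later visits. This reading is possible but unstated, so the wording still needs reconciling.

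Two further points are fair. The figures rest on an assumed event, and with one event the intervals overlap heavily (0.2% to 31.9% against 0% to 23.2% at n = 15). Technical success is defined in section B but is not among the endpoints in sections 2.5.1.1 and 2.5.1.2.

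The reply does not restore the scheduled reviews. Recording a known complication does not substitute for asking about later ones, and a silent analysis section does not guarantee that the subject is counted.

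**Conclusion.** The point holds in a limited form. Sections 2.4.2.1 and 3.3 conflict on their face. If the first is applied, subjects with a complication that prevents or stops GAE lose the scheduled adverse event reviews and KOOS and fall out of the 6-month paired comparison. The complication itself remains on record.

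Loss from the safety and technical-success denominators is possible, because no analysis set is stated, but no rule prescribes it. Were it to happen, the direction would favour GAE. One assumed event would turn a reported rate of 6.7% (n = 15) or 3.3% (n = 30) into 0%, and would lower the upper 95% limit from 31.9% to 23.2%, or from 17.2% to 11.9%.

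These sizes assume one event, a procedure stopped before embolization, and omission of the subject from the report. The loss of scheduled follow-up needs only that the withdrawal condition is applied as written. The change is worth making because it is cheap and safety is a declared purpose.

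**What to change.** Reconcile sections 2.4.2.1 and 3.3 so that failure to complete the procedure does not by itself end study data collection. This concerns retention and analysis only, and leaves clinical management of the complication untouched.

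Keep these subjects, with their agreement, in the scheduled adverse event reviews. Collecting their 6-month KOOS is optional; if it is not collected, section 2.5.3 should say how they are handled.

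In section 2.5.4, state that adverse events and technical success are reported over every subject in whom the procedure was attempted, with aborted attempts counted as technical failures. Say what counts as an attempt, for instance an attempt at arterial access.

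The cost is a protocol wording change and a few extra visits. The reported complication and technical-success rates may be slightly less favourable.

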2.5 Statistical Methods and Data Analysis

2.5.1 Study Endpoints

2.5.1.1 Primary Endpoints

The primary endpoint of this study will be overall efficacy of treatment as determined by an improvement in pain of at least 10 points based on the KOOS Pain questionnaire at 6 months. The null and alternative hypotheses respectively will be: H_0 : Mean_{GAE} = Mean_{Sham} and H_A : Mean_{GAE} \neq Mean_{Sham}, with a two sided test.

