Study Title: Geniculate Artery Embolization for the Treatment of Knee Osteoarthritis 04/08/2025

G190248 Supplement 001

A. Cover Page

Device Information : Device name: Teleflex Gel-Bead

Intended use of device:

The Gel-Bead embolization particles will be used to perform geniculate artery embolization (GAE) for the purposes of treatment of osteoarthritis-related knee pain.

Device Information:

Device name: Teleflex Gel-Bead

Intended use of device:

The Gel-Bead embolization particles will be used to perform geniculate artery embolization (GAE) for the purposes of treatment of osteoarthritis-related knee pain.

Sponsor-Investigator and Correspondent Contact Information:

[name] University of Pittsburgh Medical Center [name] [contact] / [contact] [contact]

Manufacturer Information:

Teleflex (acquired Vascular Solutions, Inc. February 2017) [name] [contact]

Distributed by Medtronic

Referenced files: There are no referenced files.

Protocol Ammendments:

Updated protocol to remove 6-minute walk test due to feasibility issues in performing

B. Clinical Plan

The primary goal of our investigation is to determine if geniculate artery embolization (GAE) will result in a decrease in pain and disability caused by knee osteoarthritis. The investigation will be conducted as two distinct studies:

 A pilot study of GAE for the treatment of knee osteoarthritis
 A series of up to 30 subjects undergoing geniculate artery embolization will be included in this arm with the explicit purpose to demonstrate safety and efficacy.

The primary endpoint of this study is overall efficacy of treatment as determined by a minimal clinically significant improvement in KOOS pain score of 10 based on the KOOS Pain questionnaire at 6 months.

Secondary outcomes will be improvement in functionality and quality of life based on the KOOS Function in Sport and Recreation, and KOOS Quality of Life Scales. Secondary outcomes will also include changes in quantitative functional metrics as well as reduction in medication use.

Technical success will be defined as the performance of diagnostic angiography of the knee with delivery of the Gel-Bead particles to a region of hypervascularity within the knee resulting in reduced flow/occlusion of the target vessels. Clinical success will be defined by a decrease in pain of 10 points per the KOOS questionnaire at 6 months.

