Remote consenting may be used as opposed to in person consenting where possible to reduce unnecessary in person encounters. In the event remote consenting is utilized, subjects will be provided with a copy of the informed consent prior to the teleconsent meeting either via email, fax, mail or previously provided during an in-person visit. After the physician investigator and subject review the consent form via video conferencing (e.g., telephone, conference call, videoconference, telemedicine, etc.), the subject will be offered the opportunity to ask any questions and have those questions answered. The subject will sign and date the informed consent.

The physician investigator will verify the subject physically signed the consent document either by viewing via video conference or obtaining a photo of the complete signed consent signature page or obtaining verbal confirmation from the subject that he/she signed the consent form or agreed to participate electronically. The signed document is then mailed, emailed, photo/scanned to text or faxed to the study team.

If the signed consent is provided as an electronic copy (emailed, photo/scanned, or faxed), the subject will return the original signed document on their first in person visit or by mail. If the signed consent form is mailed to the study team, the physician investigator will sign their copy which they possess after the subject has acknowledged signature on their copy. Once the subject's original copy is received the study team's copy will be attached to make a single document.

The study team will document the remote consent process, including the date and time the conversation occurred, how it occurred (e.g., telephone, video conference), the names of the participants, confirmation that the subject received the informed consent, and confirmation of informed consent to participate.

Visit 2 GAE Procedure:

Subjects should withhold pain medication 24 hours prior to visit for the evaluation of VAS or other measures.

Subjects will be treated with a genicular artery embolization (GAE) procedure performed with Gel Bead Microspheres. The microspheres will be delivered in a saline-contrast medium solution and will be delivered to the arteries supplying the areas of the subject's pain.

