2.5.2 Sample Size Determination

The Knee Injury and Osteoarthritis Outcome (KOOS) Score which is a primary outcome measure is a measure of patients' knee and associated problems and functionality. It is endorsed by the American Academy of Orthopedic Surgeons, the US Food and Drug Administration, and the International Cartilage Repair Society and has demonstrated reliability for both clinical and research purposes (11). The Visual Analog Scale (VAS) for pain will be used as a secondary outcome measure. This scale is also well-validated and has demonstrated reliability for patients with osteoarthritis (12). The Minimal Clinically Important Difference (MCID) for KOOS has been reported to be ~10. Data on the KOOS indicates a population standard deviation of 15 (koos.nu). Assuming we wish to detect an MCID of 10 points in this population, our targeted effect size is 0.66. A power calculation for a paired t-test (baseline vs 6-month KOOS Pain scores) shows our pilot study of 15 patients would have 22% power.

2.5.3 *Efficacy Analysis*

Comparison of semi-quantitative and quantitative outcome measures will be performed with the appropriate statistics testing. For the pilot group, baseline and endpoint scores will be compared using paired t-tests.

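### The primary endpoint is a 10-point KOOS Pain improvement, but no planned analysis estimates or tests it, and the hypothesis stated under it compares GAE with a sham group that the described series does not have.

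*Combined protocol and SAP*

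**What the plan says.** Section 2.5.1.1 describes the primary endpoint as overall efficacy "determined by an improvement in pain of at least 10 points based on the KOOS Pain questionnaire at 6 months". The Clinical Plan (section B) states the same endpoint and adds: "Clinical success will be defined by a decrease in pain of 10 points per the KOOS questionnaire at 6 months".

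Directly after the endpoint, 2.5.1.1 gives the hypothesis to be tested, two-sided: "The null and alternative hypotheses respectively will be: H_0 : Mean_{GAE} = Mean_{Sham" (the alternative is that the two means differ).

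The design text describes one treated series. Section B and 2.2.1 speak of a series of patients undergoing embolization, and the Visit 2 text in 2.4.1 says: "Subjects will be treated with a genicular artery embolization (GAE) procedure performed with Gel Bead Microspheres". Section B also announces that "The investigation will be conducted as two distinct studies", but only the pilot is listed.

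The only test named for the pilot is in 2.5.3: "For the pilot group, baseline and endpoint scores will be compared using paired t-tests". No null value is given. The section's other sentence promises appropriate testing without naming any.

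The 10 points also appear in 2.5.2, as a planning quantity: "Assuming we wish to detect an MCID of 10 points in this population, our targeted effect size is 0.66". That section gives the SD as follows: "Data on the KOOS indicates a population standard deviation of 15 (koos.nu").

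**The concern.** An endpoint defined by a threshold needs an analysis that uses the threshold: a proportion of patients reaching it, or a mean change set against it. The plan has neither. It has a hypothesis that needs a sham mean, and a test that asks whether the mean change differs from zero.

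The plan therefore does not say what result would meet its primary endpoint. If the 10 points is a property of each patient, a paired t-test does not show how many patients reached it. If it is a property of the mean, the test can be significant with a mean below it. The plan also does not say how patients without a 6-month score count, although 2.4.2.1 withdraws patients who significantly escalate conservative therapy. If these choices stay open until 6-month scores are seen, the more favourable reading can be selected afterwards.

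**Working it through.** **Inputs from the documents.** Target difference 10 and population SD 15 (2.5.2). Sample size 15 (2.2.1, 2.5.2, 3.1), or 30 (2.3.2; up to 30 in section B). Two-sided test (2.5.1.1).

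**Assumptions.** Significance level 0.05, which the documents state only for adverse events (2.5.4). The SD of the change is not given. If baseline and 6-month scores each have SD 15 and correlation ρ, it is 15·√(2(1−ρ)): 15 at ρ = 0.5 and 21.2 at ρ = 0. I use 12, 15 and 21.2.

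**The plan's own figures.** The effect size is 10/15 = 0.667, printed as 0.66, which agrees apart from truncation. The stated 22% power does not reproduce: a paired t-test with n = 15, effect size 0.66 to 0.667 and two-sided 0.05 has 66% to 67% power. That is a separate matter, and nothing below depends on it.

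**Smallest observed mean change that the paired t-test calls significant** = t(0.975, n−1) × SD/√n.

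| n | t | SD 12 | SD 15 | SD 21.2 |
|---|---|---|---|---|
| 15 | 2.145 | 6.6 | 8.3 | 11.7 |
| 30 | 2.045 | 4.5 | 5.6 | 7.9 |

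For example, at SD 15: 2.145 × 15/√15 = 8.3, and 2.045 × 15/√30 = 5.6.

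**Where the threshold reaches 10.** Solving for the SD gives 10·√15/2.145 = 18.06 at n = 15 and 10·√30/2.045 = 26.8 at n = 30. With 30 patients, a significant result with a mean below 10 is possible at every SD in the table. With 15 patients it is possible at 12 and 15 but not at 21.2.

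**Per-patient reading.** Suppose changes are normal with SD 15 and the mean sits exactly at the significance threshold. The share improving by at least 10 is 1 − Φ((10 − 8.31)/15) = 45.5% at n = 15, and 1 − Φ((10 − 5.60)/15) = 38.5% at n = 30. In both cases the test is just significant while fewer than half of patients reach clinical success. The plan does not say whether that would count as meeting the endpoint.

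**Sham hypothesis.** It needs two means. The design text supplies one treated group and no external sham value, so the hypothesis as written has no data.

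**Precision of the missing estimate.** Exact (Clopper-Pearson) 95% intervals: 15 of 30 responders gives 31% to 69%; 8 of 15 gives 27% to 79%.

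**The case against.** Several points on the other side stand, and they limit the claim.

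- *The 10 points are not idle.* A reader might infer that no success definition uses them. Section B does define clinical success by 10 points, and 2.5.2 uses 10 as the difference to detect. What is missing is an analysis of that success and a criterion at trial level.
- *The unit is less open than it looks.* Section B sets clinical success beside technical success, which is described for a single procedure. That favours a per-patient reading, although the text does not say so.
- *Testing against zero while sizing on a target difference is common.* An adequately powered test normally becomes significant below the target. A reader might take the chance of significance with a mean below 10 as a false-positive rate. It is not one. As an illustration at n = 30 and SD 15, that chance (counting improvements only) is 39% if the true mean change is 5 and 44% if it is exactly 10, so it does not separate a weak effect from one on target.
- *The sham hypothesis may belong elsewhere.* Section B announces two studies, 2.5.4 compares groups and the design figure is not shown. A reader might infer that a sham arm was dropped, or that the hypothesis must be deleted. The documents establish neither; they show only that it cannot apply to the series described.
- *This is a pilot.* That is a good reason not to demand a pass/fail cutoff. It does not remove the need to estimate the stated primary endpoint, since section B and 2.2.1 give demonstrating safety and efficacy as the purpose.

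**Conclusion.** The concern holds in this form: the plan states a 10-point endpoint and a 10-point definition of clinical success, but plans no analysis that estimates or tests that success, and its stated hypothesis cannot be tested in the single treated series described. This gap follows from the text and depends on no assumed number.

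The numerical part, that the named test can be significant at a mean change below 10, depends on the unknown SD of change and on the assumed 0.05 level. At SD 15 the threshold is about 8.3 points (n = 15) or 5.6 (n = 30). Across SDs of 12 to 21.2 it is 6.6 to 11.7 at n = 15 and 4.5 to 7.9 at n = 30. With 15 patients and an SD above about 18, this numerical conflict on the mean disappears; the missing analysis of the 10 points does not. The plan should be amended, but the finding does not show that the study would reach a wrong conclusion.

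**What to change.** Amend the statistical section before 6-month outcome data are reviewed.

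1. In 2.5.1.1, replace the GAE-versus-sham hypothesis with a single-arm statement on change in KOOS Pain from baseline to 6 months, or state that the sham hypothesis does not apply to the pilot.
2. State that the 10 points applies per patient, consistent with clinical success in section B, or state otherwise. Report the proportion improving by at least 10 points with an exact 95% CI. Name the denominator, because 2.3.2 defines enrolment by consent and 2.4.2.1 allows withdrawal when the procedure cannot be performed or completed. Give the number without a 6-month score, and show the result both with those patients counted as non-responders and among completers.
3. Report the mean change with its 95% CI alongside the 10-point MCID. Keep the paired t-test as evidence of change from zero only.

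No pass/fail cutoff is required; the results can be presented as estimates.

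**Cost.** A dated amendment and no new data, because KOOS is already collected at screening and at 6 months. The price is an imprecise proportion, as the intervals above show, and an efficacy statement that may be less favourable. The version dates (4/18/2023 in section 2.0, 04/08/2025 on the first page) suggest that the study may be under way, which is an inference. Any criterion added after 6-month data have been seen should be labelled post hoc.

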2.5.4 Safety Analysis

Differences in the occurrence of adverse events between groups will be assessed with chi-square tests with a significance level p < 0.05. Descriptive statistics will be used to report occurrence of adverse events in the pilot group.

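### The primary hypothesis compares GAE with sham, but the trial described has no sham arm and plans a paired before/after test

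*Combined protocol and SAP*

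**What the plan says.** Section 2.5.1.1 defines the primary endpoint as "an improvement in pain of at least 10 points based on the KOOS Pain questionnaire at 6 months". It then states the only formal hypothesis in the plan: "The null and alternative hypotheses respectively will be: H_0 : Mean_{GAE} = Mean_{Sham", with a two-sided alternative that the two means differ. It assigns this to the primary endpoint of the present study.

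The design text describes a single treated group. Section 2.2.1 reads "A series of 15 patients undergoing geniculate artery embolization will be included in this arm with the explicit purpose to demonstrate safety and efficacy". Visit 2, under section 2.4.1, reads "Subjects will be treated with a genicular artery embolization (GAE) procedure performed with Gel Bead Microspheres". Sections B and 3.1 also describe one treated series. No sham procedure, randomisation, allocation or blinding appears in the readable text.

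The analysis text is also single-group. Section 2.5.2 says "A power calculation for a paired t-test (baseline vs 6-month KOOS Pain scores) shows our pilot study of 15 patients would have 22% power", and section 2.5.3 says "For the pilot group, baseline and endpoint scores will be compared using paired t-tests".

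Some two-group wording remains. Section B announces that "The investigation will be conducted as two distinct studies" but lists only the pilot. Section 2.5.4 says "Differences in the occurrence of adverse events between groups will be assessed with chi-square tests with a significance level p < 0.05", and its next sentence plans descriptive adverse-event reporting for the pilot.

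**The concern.** One endpoint carries three different targets: a difference from sham (the hypothesis), a mean change different from zero (the paired test), and a gain of at least 10 points (the definition of efficacy). Only the second can be tested as planned. No sham mean will be observed, so no result from this trial can reject or retain the stated null.

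The stake is interpretation. If the paired p-value is reported against the written hypothesis, a before/after change will be read as an effect over sham. Natural fluctuation, placebo response to an invasive procedure and regression to the mean would then be credited to the device. Regression to the mean is plausible because section 2.3.3 selects patients on VAS pain of 30 to 100 mm. The rules against starting or escalating pain therapy (Visit 2 and section 2.4.2.1) limit co-intervention, but not these other sources. A significant paired test also does not show that the 10-point criterion was met.

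**Working it through.** **Inputs.** From the documents: difference of interest 10 points, SD 15 and effect size 0.66 (section 2.5.2); n = 15 (sections 2.2.1, 2.5.2, 3.1) or 30 (section 2.3.2; up to 30 in section B); two-sided test (section 2.5.1.1). Assumed: alpha 0.05, which the plan states only for the safety test. The plan gives no SD of change and no expected placebo response.

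**The plan's own power figure.** All power values use the noncentral t distribution.

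- Paired test, n = 15, d = 0.66: noncentrality 0.66 × √15 = 2.56 on 14 df gives 66.2%, not the stated 22%. At n = 30 it gives 93.7%.
- Two-group test with 15 patients split 7 and 8: noncentrality 0.66 × √(7 × 8 / 15) = 1.28 on 13 df gives 21.9%, which matches 22%.
- For a paired test with n = 15 to have 22% power, the SD of change would have to be about 30.5. With SD 15 per visit, SD of change = 15 × √(2(1 − ρ)), so ρ = 1 − 30.47² / 450 = −1.06, which is impossible.

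The stated power thus fits a two-group comparison like the hypothesis, although section 2.5.2 labels it paired. That it is left over from a two-group design is an inference.

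**What the paired test can and cannot show.** Take 15 as the SD at each visit. Correlation 0.5 gives SD of change 15 × √1 = 15, and correlation 0 gives 15 × √2 = 21.2. The smallest mean change reaching p<0.05 is t(0.975, n−1) × SD / √n. The last two columns give the chance of p<0.05 when the true mean gain is entirely non-specific. The 5 and 8 points are illustrative and not taken from the documents.

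| n | SD of change | Smallest significant mean change | p<0.05 if true gain is 5 | p<0.05 if true gain is 8 |
|---|---|---|---|---|
| 15 | 15 | 8.3 | 22.5% | 48.5% |
| 30 | 15 | 5.6 | 42.3% | 80.6% |
| 15 | 21.2 | 11.7 | 13.6% | 27.5% |
| 30 | 21.2 | 7.9 | 23.9% | 51.5% |

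In three of the four rows the test can be significant with a mean change below 10 points. With correlation 0.75 (SD of change 10.6), the thresholds fall to 5.9 (n = 15) and 4.0 (n = 30), and a 5-point gain is significant in 40% to 70% of trials.

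**The case against.** The strongest reply is that the analysis to be run is not in doubt. Section 2.5.3 names the paired t-test for the pilot, section 2.5.4 plans descriptive safety reporting for it, and nowhere does the plan say it will present the paired result as an effect over sham. The sham sentence may belong to the unlisted second study. The design figure in section 2.2 is not available, section 2.2.2 has no text, and arm and group wording occurs in sections 2.2.1, 3.1 and 3.2.3. A comparative stage could therefore exist elsewhere. This may explain the sentence but does not repair it: section 2.5.1.1 attaches it to this study's primary endpoint, and the pilot is left without a hypothesis of its own.

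Two narrower points stand. First, the rejection rates describe any uncontrolled before/after test and would be the same after the hypothesis is reworded. They show the cost of misreading the result, not an error rate created by the wording, and they depend on the chosen gains and SDs. Second, the 66.2% treats 15 as the SD of change. If 15 is the SD at one visit, a 10-point change has 40% to 92% power at n = 15 for correlations of 0 to 0.75.

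The wrong power figure and the conflict between 15 and 30 patients are separate defects. They matter here because the restated hypothesis needs a power statement of its own.

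**Conclusion.** The concern holds, and the plan must be corrected on this point. The primary hypothesis needs a sham mean, the text describes 0 sham patients, and the named test addresses a different null. This conclusion rests on the text alone and needs no numerical assumption.

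The size of the interpretive risk does rest on assumptions: two-sided alpha 0.05, n of 15 to 30, and SD of change of 15 to 21.2. On those, a purely non-specific gain of 5 points is significant in 14% to 42% of trials and one of 8 points in 28% to 81%. Significance is possible below 10 points in three of the four cases. A higher correlation between visits makes this easier. The chi-square sentence in section 2.5.4 is a smaller leftover of the same kind.

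**What to change.** - **Section 2.5.1.1:** state H0 as mean change in KOOS Pain from baseline to 6 months = 0, against a two-sided alternative, tested by the paired t-test at a stated alpha.
- **The 10-point criterion:** report the mean change with its 95% CI read against 10 points, and the proportion of patients gaining at least 10 points with an exact 95% CI (for example 9/15: 32.3% to 83.7%; 18/30: 40.6% to 77.3%). The responder summary builds on section B, which already defines clinical success by 10 points. State that p<0.05 alone does not meet the criterion.
- **Scope of the claim:** state that the pilot estimates within-patient change and not an effect over sham.
- **Section 2.5.4:** delete the between-group chi-square sentence, or label it as belonging to a separate study. Keep the descriptive reporting and add exact 95% CIs (upper limit with no events: 21.8% for 0/15, 11.6% for 0/30).
- **Section B:** explain or remove the reference to a second study.
- **Section 2.5.2:** recompute power for the restated hypothesis at a reconciled n, and say whether 15 is the SD of the change or of a single visit.

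The cost is protocol wording and one recalculated power figure, with no new data. The price is a more modest efficacy claim.
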